### **13.0 Criteria For Removal From Study**

13.1 If at any time the patient develops grade 4 toxicity (other than controllable fever, vomiting, headache) attributed to the study drugs, he/she will be removed from study and receive no further injections.

13.2 If at any time the patient is found to be ineligible for the protocol as designated in the section on Criteria for Patient/Subject Eligibility (i.e., a change in diagnosis), the patient will be removed from the study.

13.3 If at time disease progression is observed, the patient will be removed from the study.

13.4 If the patient experiences adverse events, including unacceptable toxicity or exacerbation of underlying disease associated with drug administration and necessitating discontinuation of treatment, he/she will come off the study. Patients who are removed from the study due to adverse events will be treated and followed according to established medical practice. All pertinent information concerning the outcome of such treatment will be entered in the Case Report Form or the Serious Event Report, as applicable.

13.5 Withdrawal of consent: The patient's desire to withdraw from the study may occur at any time.

13.6 Noncompliance: If at any time the patient is non-compliant with therapy, radiation safety guidelines or requests withdrawal from the study, he/she will be removed.

13.7 Pregnancy: The patient will be removed from study if they are found to be pregnant.

#### **14.0 Biostatistics**

This is a phase II study to assess the clinical efficacy of weekly intrathecal  $^{131}\text{I}$ -3F8 for a new cohort of 17 patients with GD2-expressing central nervous system and leptomeningeal neoplasms. A "response" is defined as a patient being alive six months after their first treatment. We will test hypothesis that the proportion of responses is 25% or more against a null hypothesis that proportion of responses is 5% or less, with a power of 80% and an alpha of 5%. Using a Simon two-stage optimal design, nine patients will initially be accrued. If at least one responds, then a further 8 patients will be entered on study. If the total number of responses is three or more, the agent will be declared active. Under this design, the probability of declaring the agent inactive at the end of the first stage (0 / 9 responses) is 0.63 if the true response rate is 0.05. This probability decreases to 0.08 if the true response rate is 0.25. The probability of declaring the agent active (3 or more responses / 17) is 0.05 and 0.8 if the true response rate is 0.05 or 0.25, respectively. It is expected that 4-6 patients/yr will be enrolled and that this study can be completed within 2-3 years.

	Reject null hypothesis if:	Reject alternative hypothesis if:
First stage	-	0 / 9 responses
Second stage	$\geq 3$ / 17 responses	$\leq 2$ / 17 responses

The number of CRs, PRs, SDs and PDs will be reported. Toxicities will be reported by type and grade.

Three additional subgroups will be added for patients with: Medulloblastoma in CR (36 evaluable patients), Medulloblastoma with stable, but minimal disease (36 evaluable patients), and Retinoblastoma or Melanoma (18 evaluable patients). For patients with neuroblastoma or other cancers in the CNS, 18 additional evaluable patients will be added. We have completed the statistics for this agent overall which have shown efficacy on this phase II study; increasing the number of slots will allow for in depth statistical analyses within these subgroups of patients.

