## **1.0   Protocol Summary and/or Schema**

This study is designed to test the efficacy and the cumulative toxicity of intrathecal (administered through Ommaya reservoir)  $^{131}\text{I}$ -3F8 in children and adult patients with GD2-expressing central nervous system/leptomeningeal neoplasms. Survival is extremely poor in these patients, with median survival of only a few months. In a prior phase I trial, 2 of 13 patients had negative remain alive and in complete remission after 4 years. Patients in this protocol will receive intrathecal  $^{131}\text{I}$ -3F8 weekly for a total of four treatment cycles. About 130 patients will be accrued on this study. The primary endpoint is overall survival at six months.

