## **2.1 Objectives and Scientific Aims**

- To determine whether, in patients with GD2-expressing central nervous system/leptomeningeal neoplasms, the activity of intrathecal  $^{131}\text{I}$ -3F8 is sufficiently promising to warrant further study. Promising activity is defined as a 6 month overall survival rate of 25% or more.
- To determine the response rate to  $^{131}\text{I}$ -3F8 in this population.
- To determine the cumulative toxicities of serial injections of intrathecal  $^{131}\text{I}$ -3F8.
- To describe the effects of HAMA (human-anti-mouse antibody) on cerebrospinal fluid (CSF) and serum pharmacokinetics following multiple injections of  $^{131}\text{I}$ -3F8

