## **4.1 Overview of Study/Design Intervention**

### **4.2 Design**

This is a phase II single-arm open-label study that will define responses to therapy with weekly intrathecal  $^{131}\text{I}$ -3F8 in patients with central nervous system/leptomeningeal GD2-expressing disease. Dosimetry at plaques of disease and surrounding normal tissues will be determined by a pre-treatment  $^{131}\text{I}$ -3F8 (2 mCi) scintigraphy. Pharmacokinetics of the dosimetry

dose of intrathecal  $^{131}\text{I}$ -3F8 will be determined by measurements of counts per minute (cpm) of serial CSF and serum samples.

Patients will then receive intrathecal  $^{131}\text{I}$ -3F8 treatment cycle (10 mCi/cycle) approximately weekly for a total of 4 cycles. A total dose of 40 mCi  $^{131}\text{I}$ -3F8 will be administered. Since the phase I study demonstrated a CSF dose of 15-60 cGy/mCi to the CSF, maximum total anticipated CSF dose of  $4 \times 10$  mCi of  $^{131}\text{I}$ -3F8 injections would be 600-2400 cGy; dose to the spinal cord and normal brain is negligible given the short range path length of  $^{131}\text{I}$ . At an estimated tumor to CSF dose ratio of 5:1, tumor dose could be as high as 3000-12000 cGy. Myelosuppression is not anticipated at this dose level. The chosen 40 mCi maximum  $^{131}\text{I}$  dose is considerably lower than the MTD reported using other intrathecal  $^{131}\text{I}$ -monoclonal antibodies for neoplastic meningitis on other phase I studies. To avoid the risk of radiation toxicity in patients who have had previous craniospinal radiation, the CSF radiation dose delivered by  $^{131}\text{I}$ -3F8 therapy injections will not exceed 2400 cGy based on the CSF dosimetry estimates from pre-treatment  $^{131}\text{I}$ -3F8 / scintigraphy scans. This may require the elimination and/or dose reduction of the 3rd or 4th injection for patients who have had previous craniospinal radiation. There will be no dose modifications for patients who have not had craniospinal radiation. Response to therapy will be assessed by neurologic examination, radiographic imaging and CSF cytology analysis. Other aims will be met by monitoring patients clinically and biochemically for toxicity and by serum assessment of HAMA.

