##### **4.2.1 Clinical Evaluation**

Patients will have pre- and post-treatment clinical assessment including neurologic examination, hematology and serum chemistries, and CSF analysis. Patients without objective disease progression and without unexpected grade 4 toxicity (controllable fever, headache, nausea, vomiting not included) will be eligible for a total of 4 treatment cycles. No patient will receive more than 4 treatment cycles.

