## **10.0 Evaluation During Treatment/Intervention**

### **10.1 Evaluation during treatment**

10.1.1. Physical exam prior to each injection and after the 4th injection

10.1.2. Neurologic exam prior to each injection and after the 4th injection

- 10.1.3. MRI of head and spine at baseline and after 4th injection
- 10.1.4. CSF Flow study prior to the first injection
- 10.1.5. CBC with differential including platelets prior to each injection and ~1-3 months after 4th injection
- 10.1.6. Comprehensive profile to each injection and ~1-3 months after 4th injection.  
 \*Thyroid protection such as SSKI and Cytomel will be adjusted to ensure adequate thyroid saturation. Serum HAMA (send to [name]) prior to each injection.
- 10.1.7. B-HCG for females of child-bearing age prior to injections 1 and 3.
- 10.1.8. CSF and Blood (2 ml each sample) at ~1-4 hr, 18-24 hours, and 42-48 hours after the I-3F8 dosimetry injection

Observation	Prior to test dose with  I-3F8	Post test dose with  I-3F8	Prior to 1st injection	Post 1 st  I-3F8 Injection	Prior to 2 nd  I-3F8 injection	Post 2 nd injection	Prior to 3 rd  I-3F8 injection	Post 3 rd injection	Prior to 4 th  I-3F8 injection	Follow-up, 1-3 months after 4 th injection
Physical examination	X		X		X		X		X	X
Neurologic examination	X		X		X		X		X	X
MRI head	X									X
MRI spine	X									X
CSF flow study	X									
CBC w/diff, plts	X		X		X		X		X	X
Comprehensive profile	X		X		X		X		X	X
CSF cytology	X									X
Serum HAMA	X		X		X		X		X	
B-HCG (when applicable)	X						X			
Scintigraphy imaging  I-3F8		X								
CSF and Blood (2ml/sample)  I-3F8	X									

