## 11.0 Toxicities/Side Effects

11.1 Toxicities will be assessed via the NCI toxicity criteria (CTC 3.0). All toxicities will be recorded in CRDB until 30 days after the last dose of  $^{131}\text{I}$ -3F8.

11.2 Toxicities associated with  $^{131}\text{I}$ -3F8 include fever, headache, nausea and vomiting, pain, allergic reaction, and/or drug extravasation. Hospitalizations for therapy administration, hyperglycemia or lymphopenia related to dexamethasone and self-limited fever, vomiting, or headache will not be considered serious adverse events (SAE) and will not be reported to the IRB or FDA though they will be captured in the institutional database. However, life-threatening infections or other life-threatening side effects will be considered SAE's and will be promptly reported to the Institutional Review Board of MSKCC and to the FDA.

11.3 Neurologic changes during the study period which meet the criteria for grade 4 neurotoxicity will be assessed by study physicians as being unrelated, possibly or probably caused by the injection. In the absence of clear evidence of tumor progression, it may be assumed that new signs and symptoms are treatment related.

11.4 Any deaths will be reviewed during the study by the Principal Investigators prior to subsequent entry of further patients.

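### Cumulative toxicity over repeated injections is a study aim, but the planned toxicity summary has neither injection number nor number of patients treated

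*Combined protocol and SAP*

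**What the plan says.** Section 1.0 names cumulative toxicity next to efficacy as what the study tests. The third objective in section 2.1 reads "To determine the cumulative toxicities of serial injections of intrathecal" 131I-3F8.

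On analysis, section 14.0 has one sentence: "Toxicities will be reported by type and grade". Section 4.2 adds only how the aim is to be observed: "Other aims will be met by monitoring patients clinically and biochemically for toxicity and by serum assessment of HAMA". Section 11.1 gives the grading scale (CTC 3.0) and a recording window that closes 30 days after the last dose.

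Exposure is repeated and varies between patients:
- After a dosimetry injection, treatment runs to four cycles. Section 4.2.1 sets the ceiling: "No patient will receive more than 4 treatment cycles".
- Under 13.1, a patient with attributed grade 4 toxicity (some events excepted) leaves: "he/she will be removed from study and receive no further injections". Under 13.3, progression also ends participation.
- After earlier craniospinal radiation, injection 3 or 4 may be reduced or omitted (4.2, 9.3.1).
- Section 12.1 counts two treatment injections as an adequate trial.

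**The concern.** An aim about serial injections needs a summary in which the series is visible. A table by type and grade pools all injections, so a toxicity seen mostly after injection 4 looks the same as one spread evenly over the course. It also pools patients who had one or two injections with those who had four. The people reaching the later injections are fewer and selected, because those who progressed or had attributed grade 4 toxicity have already left.

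At stake is what the trial can say about its four-injection schedule. Section 3.4 (preliminary phase II results) sets the goal of shortening the interval between injections while lowering toxicity, and section 1.0 plans about 130 patients. Whether later injections carry more toxicity than earlier ones is a natural question for such a schedule, and the plan as written produces no summary that bears on it.

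**Working it through.** **1. The plan's own figure.** There is none. The documents state no toxicity rate, threshold, sample size or error rate. The alpha of 5% and power of 80% in 14.0 belong to the survival endpoint.

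**2. Aim against analysis.** The sections that mention toxicity (1.0, 2.1, 3.4, 4.2, 4.2.1, 9.3.1, 11.0, 13.0, 14.0, 17.2.1) were read for any summary by injection number, cumulative activity or CSF dose, number of patients treated at each injection, or time. None gives one. Section 4.2 describes monitoring, section 11 grading and recording, section 13 removal of individual patients and section 17.2.1 SAE reporting.

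**3. Can the planned table show a change over injections?** The rates here are assumed. Every patient is taken to receive four injections, and r_k is the risk of a first event at injection k among patients without an earlier one. The share of patients with any event is

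1 − (1 − r1)(1 − r2)(1 − r3)(1 − r4)

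| Assumed r1 to r4 | Calculation | Patients with an event |
|---|---|---|
| 5%, 5%, 5%, 5% | 1 − 0.95^4 = 1 − 0.8145 | 18.5% |
| 2%, 4%, 6%, 8% | 1 − 0.98 × 0.96 × 0.94 × 0.92 = 1 − 0.8136 | 18.6% |
| 10%, 10%, 10%, 10% | 1 − 0.90^4 = 1 − 0.6561 | 34.4% |
| 2%, 6%, 12%, 20% | 1 − 0.98 × 0.94 × 0.88 × 0.80 = 1 − 0.6485 | 35.1% |

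Within each pair, the flat and the rising pattern are nearly indistinguishable at patient level.

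**4. Does a breakdown by injection help?** Take 100 assumed patients, all given four injections, with 40 events of one type and grade. Flat counts of 10, 10, 10, 10 and rising counts of 2, 6, 12, 20 both sum to 40. For a linear trend with scores 1 to 4 and pooled rate 40/400 = 0.10, treating injections as independent:
- Rising: T = 1(2 − 10) + 2(6 − 10) + 3(12 − 10) + 4(20 − 10) = 30. V = 0.10 × 0.90 × (3000 − 1000²/400) = 45. z = 30/√45 = 4.47.
- Flat: T = 0, so z = 0.

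The information lies in the split by injection. The test only measures the contrast and is not proposed for the trial.

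**5. Why numbers treated are needed as well.** Suppose 100, 80, 60 and 40 patients receive injections 1 to 4 (assumed), with 12 events at each. The counts look flat, but the rates are 12/100 = 12%, 12/80 = 15%, 12/60 = 20% and 12/40 = 30%.

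**6. Is the information there?** Section 10.1 schedules "Physical exam prior to each injection", and likewise neurologic examination, blood counts and chemistry. The study database holds all toxicities (11.1). An event date is listed as a required field only for SAE reports (17.2).

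**The case against.** The strongest reply is that cumulative toxicity is never defined. It may mean the total toxicity accrued over the course, and a table by type and grade goes a good way towards describing that. The aim is also secondary and descriptive, the planned sentence does not forbid a breakdown by injection, and assessments before each injection mean the information is not obviously lost. All of this stands. It limits the point to one of specification. It does not remove it, because even the total-burden reading leaves out how many injections lay behind each patient's worst grade.

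Three stronger readings are tempting, and the documents do not support them.
- A reader might infer that the plan cannot answer the toxicity aim at all. With the term undefined, that goes too far.
- A reader might take the ten patients given four injections and the three who progressed after one (section 3.4) as 13 patients with three early stops, and infer that injection-4 rates would be understated by 13/10 = 1.3. The section gives no total of 13 and does not say that the three stopped. They were already progressing at enrolment, whereas 14.0 adds 36 medulloblastoma patients in complete remission and 36 with stable, minimal disease. Nor does the plan propose dividing injection-4 events by all patients.
- A reader might conclude that a competing-risk analysis by injection, mCi and CSF dose is required. That is more than a descriptive secondary aim needs. Activity per injection is largely fixed, so mCi mostly repeats injection number, and event dates for non-serious toxicities are not shown to be collected.

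**Conclusion.** The point holds as a gap in the analysis plan. The stated summary can describe total burden. It cannot show whether toxicity changes with repeated injections, and it ignores differences in the number of injections received.

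No size can be estimated from the documents. The near-equality of 18.5% and 18.6% rests on assumed rates and on all patients receiving four injections. It shows that the planned table cannot tell the patterns apart. It does not show that toxicity accumulates. The survival endpoint, the two-stage design and the removal rules for individual patients are untouched.

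**What to change.** In 14.0, replace the toxicity sentence with text such as:

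> The type and grade of toxicities will be tabulated separately for the test dose and for each of injections 1 to 4, with the number of patients given that injection as denominator. Worst grade per patient will also be tabulated by total number of injections received.

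Add a short note that:
- defines cumulative toxicity;
- says that rates at later injections describe a selected group and will have wide intervals;
- assigns delayed effects under weekly dosing to the most recent injection, and points out that the last injection is then observed for up to 30 days, against about 7 days for the others when dosing is weekly;
- notes that systemic chemotherapy may be given between injection 2 and injection 3 or 4 (10.5), so later toxicities may have another source.

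Confirm that onset dates of non-serious toxicities are captured. If they are not, add that field.

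No formal trend test is needed. The cost is one paragraph and one extra table, plus possibly one data field. The drawback is that late-injection rates will be imprecise and should not be over-read.

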#### **15.1 Research Participant Registration and Randomization Procedures**

#### **15.2 Research Participant Registration**

Confirm eligibility as defined in the section entitled Inclusion/Exclusion Criteria. Obtain informed consent, by following procedures defined in section entitled Informed Consent Procedures. During the registration process registering individuals will be required to complete a protocol specific Eligibility Checklist. The individual signing the Eligibility Checklist is confirming whether or not the participant is eligible to enroll in the study. Study staff are

responsible for ensuring that all institutional requirements necessary to enroll a participant to the study have been completed. See related Clinical Research Policy and Procedure #401 (Protocol Participant Registration).

15.2 Potential risks are outlined above. Procedures to minimize potential risks include prophylactic treatment with acetaminophen, dexamethasone, SSKI drops, liothyronine.. Procedures to minimize radiation exposure to self and others will be in accordance to Radiation Safety Guidelines.

15.3 Enrollment in this protocol is voluntary. In the event of adverse effects, standard medical intervention will be offered where appropriate.

15.4 All hospital records are confidential. The patient's name or any other personal identification will not be used in reports or publications from this study. Laboratory tests, images and X-rays, if any, may be published. The Food and Drug Administration or other authorized agencies (i.e. the National Cancer Institute) may inspect records. Data will be collected and stored in the patient's hospital chart and research file, and be monitored by the principal investigators to ensure the safety of patients.

15.5 There is no extra cost to the patient for being part of this study. If there is an injury as a result of this research study, emergency care, hospitalization and outpatient care will be made available by Memorial Hospital and billed to the patient as part of medical expenses. No money will be provided by the Hospital as compensation for a research-related injury.

**15. 6 Randomization**  
NOT APPLICABLE

**16.0 Data Management Issues**

A Research Study Assistant (RSA) will be assigned to the study. The responsibilities of the RSA include project compliance, data collection, abstraction and entry, data reporting, regulatory monitoring, problem resolution and prioritization, and coordinate the activities of the protocol study team.

The data collected for this study will be entered into a secure database. Source documentation will be available to support the computerized patient record.

**16.1 Quality Assurance**

Weekly registration reports will be generated to monitor patient accruals and completeness of registration data. Routine data quality reports will be generated to assess missing data and inconsistencies. Accrual rates and extext and accuracy of evaluations and follow-up will be monitored periodically throughout the study period and potential problems will be brought to the attention of the study team for discussion and action

Random-sample data quality and protocol compliance audits will be conducted by the study team, at a minimum of two times per year, more frequently if indicated.

## **17.0 Protection of Human Subjects**

The investigators agree to conduct this study in accordance with the International Conference of Harmonization (ICH) principles of Good Clinical Practice and with the Declaration of Helsinki (1989). The investigators will conduct all aspects of this study in accordance with all national, state, and local laws of the applicable regulatory agencies. Patients will be both children and adults. Patients of both sexes and all ethnic background are eligible for this study. Alternatives to this study include conventional chemotherapy, radiation therapy, or other phase I agents. Patients are responsible for the costs of physician visits and usual laboratory tests, hospitalizations and outpatient care. If there is an injury as a result of this research study, emergency care, hospitalization, and outpatient care will be made available by Memorial Hospital and billed to the patient as part of the medical expenses. No money will be provided by Memorial Hospital as compensation for research-related injury. Patient will not be billed for the antibody 3F8.

As part of standard care for this medical condition, the patient will be charged for:

- \*any needed hospitalization
- \*doctor's care
- \*any other drugs besides  $^{131}\text{I}$ -3F8 needed for treatment
- \*standard laboratory tests, but not pharmacokinetic studies
- \*standard radiographic studies
- \*clinic visits

### **17.1 Privacy**

MSKCC's Privacy Office may allow the use and disclosure of protected health information pursuant to a completed and signed Research Authorization form. The use and disclosure of protected health information will be limited to the individuals described in the Research Authorization form. A Research Authorization form must be completed by the Principal Investigator and approved by the IRB and Privacy Board.

